8.1.3 In-Lab *QuickSIN Test - Validity* (initial Pro-Fit vs. initial Self-Fit A)

- i. Paired-sample t-test for equivalence of the means of the initial-fit settings of the SELF-FIT A procedure to initial-fit settings of the PRO-FIT procedure
- ii. Supplementary analyses will include examination of the distribution of differences in dB between the QuickSIN threshold SNRs for initial-fit settings of the SELF-FIT A procedure and the initial-fit settings of the PRO-FIT procedure, as well as computation of correlation coefficients between the threshold SNRs for each method.

8.1.4 Wear-Time Field Trial - *Validity: APHAB* (final PRO-FIT vs. final SELF-FIT A)

- i. Non-Inferiority t-Test for 2 (wear-time sequences) X 2 (fit conditions)
- ii. Supplementary analyses will include examination of the distribution of differences between the APHAB-global scores for final-fit settings of the SELF-FIT A procedure and final-fit settings of the PRO-FIT procedure, as well as computation of correlation coefficients between the two measures. Datalogging will also provide details of the subject's adjustment of the devices during each segment of the cross-over wear-time trial.

8.1.5 Wear-Time Field Trial - *Validity: QuickSIN* (final PRO-FIT vs final SELF-FIT A)

- i. Non-Inferiority t-Test for 2 (wear-time sequences) X 2 (fit conditions)
- ii. Supplementary analyses will include examination of the distribution of differences in dB between the QuickSIN threshold SNRs for final-fit settings of the SELF-FIT A procedure and the final-fit settings of the PRO-FIT procedure, as well as computation of correlation coefficients between the threshold SNRs for each method.

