3.1.2 In-lab validation component-Secondary

- Null hypothesis: Mean $|QuickSIN_{PRO-FIT} - QuickSIN_{SELF-FIT}| \geq 1.5$ dB
- Alternative hypothesis: Mean $|QuickSIN_{PRO-FIT} - QuickSIN_{SELF-FIT}| < 1.5$ dB

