3.1.4 Wear-Time Field Trial-Secondary

- Null hypothesis: Mean difference $(QuickSIN_{PRO-FIT} - QuickSIN_{SELF-FIT}) \geq 1.5$ dB
- Alternative hypothesis: Mean difference $(QuickSIN_{PRO-FIT} - QuickSIN_{SELF-FIT}) < 1.5$ dB

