3.2.3 Secondary Effectiveness Endpoints

For the validation component of the immediate in-lab session comparison, aided QuickSIN performance will be compared between SELF-FIT and PRO-FIT.

- Success criterion is the SELF-FIT QuickSIN speech-recognition threshold in noise (signal-to-noise ratio, SNR) is equivalent to that of PRO-FIT.

For the reliability component of the immediate in-lab session comparison, QuickSIN performance will be measured twice (A, B) using the SELF-FIT method to assess test-retest reliability.

- Success criterion is QuickSIN thresholds are equivalent for SELF-FIT A and B.

For the wear-time crossover field trial, QuickSIN performance will be compared between SELF-FIT and PRO-FIT.

- Success criterion is defined as SELF-FIT QuickSIN SNR is equivalent to PRO-FIT QuickSIN SNR following completion of the wear-time field trial.

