6.2.7 QuickSIN

The subject will be seated in a sound-attenuated booth facing a single loudspeaker. All QuickSIN measures, unaided and aided, will be binaural. The QuickSIN test consists of lists of six sentences that will be played from that loudspeaker at a constant level of 65 dB SPL (at location of subject's head using the method of substitution). This speech level was chosen as one approximating a typical conversational level (60-65 dB SPL) and matching the speech input level used for the REAR measures (65 dB SPL). The level of the co-located background four-talker babble increases across the six sentences for signal-to-noise ratios (SNRs) ranging from +25 to 0 dB SNR (in steps of 5 dB). The subject is asked to repeat each sentence. The audiologist scores whether the subject correctly repeated the predetermined key words in each sentence. The resulting score is interpreted as an SNR loss where a value near 0 indicates better hearing and larger values indicate more difficulty listening in noise.

There are 18 lists of the QuickSIN, but McArdle and Wilson (2006) found four of these to be non-equivalent to the others. The remaining 14 lists will be used as follows. Before the first QuickSIN measure at the end of the initial screening (Visit 1), two lists will be presented as practice lists (Lists 4 and 5). For the remaining 12 lists (Lists 1-3, 6, 8-12, 15, 17, 18), two will be assigned to each of the following conditions: unaided (during initial screen; to permit measures of relative benefit), in-lab initial SELF-FIT A, in-lab initial SELF-FIT B, in-lab initial PRO-FIT (the condition order and list pair assigned for each condition will be randomized for each participant), at end of first 10-to-14-day wear period (Visit 2; either final SELF-FIT A or final PRO-FIT), and at end of

final 10-to-14-day wear period (Visit 3; either final PRO-FIT or final SELF-FIT A). Each QuickSIN score will be based on two lists, 60 keywords, and no lists will be repeated for a given subject.

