6.2.7.1 QuickSIN Test Procedure

Four conditions: **Unaided, Self-Fit A, Self-Fit B, Pro-Fit**

- i. Listener will sit in a chair in the center of a sound-treated booth facing the speaker from which the test materials will be elicited (0 degrees azimuth, 1 meter distance).
- ii. Training: To familiarize subjects with the speech task, listeners will be presented with two practice lists (Lists 4 and 5) before commencing with the experimental protocol (Visit 1, Unaided only).
- iii. The test will be presented in a sound field at 65 dB SPL.
- iv. There are six sentences in each list of the QuickSIN and 5 keywords that are scored per sentence, resulting in a total of 30 keywords scored per list. Speech levels are automatically presented at SNRs of +25, +20, +15, +10, +5 and 0 dB, one SNR per sentence. The signal-to-noise ratio (SNR) for which 50% of the presented words are intelligible is calculated by subtracting the number of words correct (out of 30) for a given list from 25.5 (Killion *et al.*, 2004).
- v. The microphone setting will be set to "Wide" (omni-directional) during these measurements.

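### Wear-time QuickSIN (secondary endpoint): the criterion is equivalence but the hypotheses and test are one-sided, and the sign in section 3.1.4 lets a worse SELF-FIT pass

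*Combined protocol and SAP*

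**What the plan says.** **Criterion.** Section 3.2.3, for the wear-time crossover: "Success criterion is defined as SELF-FIT QuickSIN SNR is equivalent to PRO-FIT QuickSIN SNR following completion of the wear-time field trial". The synopsis says the same.

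**Hypotheses.** Section 3.1.4 gives "Null hypothesis: Mean difference $(QuickSIN_{PRO-FIT} - QuickSIN_{SELF-FIT}) \geq 1.5$ dB" and "Alternative hypothesis: Mean difference $(QuickSIN_{PRO-FIT} - QuickSIN_{SELF-FIT}) < 1.5$ dB". The difference is signed and bounded on one side. The in-lab counterpart in 3.1.2 uses an absolute value: "Alternative hypothesis: Mean $|QuickSIN_{PRO-FIT} - QuickSIN_{SELF-FIT}| < 1.5$ dB".

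**Test.** Section 8.1.5 names a "Non-Inferiority t-Test for 2 (wear-time sequences) X 2 (fit conditions") and does not restate the contrast, the margin or the significance level.

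**Objective.** The closing paragraphs of 1.5.3.1 and 8.4 ask for equivalence in the lab session and non-inferiority in the wear-time trial.

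**Direction of the score.** Section 6.2.7 says "a value near 0 indicates better hearing and larger values indicate more difficulty listening in noise". Section 6.2.7.1 agrees: the score "is calculated by subtracting the number of words correct (out of 30) for a given list from 25.5", so fewer words correct gives a higher score.

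**The concern.** There are two separate faults.

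First, the criterion and the test do not match. A one-sided bound cannot establish equivalence, because it leaves the other side open. The plan draws this distinction itself: for the in-lab QuickSIN comparisons, the absolute-value hypotheses in 3.1.2 and 3.1.6 go with equivalence tests in 8.1.1 and 8.1.3. Among the QuickSIN comparisons, only the wear-time one pairs an equivalence criterion with a one-sided test.

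Second, the one side that 3.1.4 bounds is the wrong one. If SELF-FIT is worse, its score is higher and PRO-FIT minus SELF-FIT is negative. Every negative value lies inside the alternative. As written, the hypothesis is therefore not a non-inferiority hypothesis for SELF-FIT either.

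At stake is the only formal comparison of speech-in-noise performance after wear. Programmed literally, it could report success for a SELF-FIT well outside the 1.5 dB margin. Corrected only after the data are seen, it would be a post hoc change in a study meant to support a 510(k) submission.

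**Working it through.** **Inputs.** Margin 1.5 dB (3.1.4); N = 36 (5.1). No SD, significance level or power is stated for this endpoint. I carry over the one-sided 2.5% that 5.1 states for the APHAB, and assume an SD of within-subject differences of 2 to 3.5 dB. The 0.05 in the synopsis refers to the in-lab comparisons.

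**Step 1: reproduce the plan's own figure.** Section 5.1 gives 80% power for the APHAB with N = 32, margin 0.084, true difference 0 and √MSE 0.115.
- SD of differences = 0.115 × √2 = 0.163
- SE = 0.163 / √32 = 0.0288
- Noncentrality = 0.084 / 0.0288 = 2.92; critical t on 30 df = 2.042
- Power by noncentral t = 0.805

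This agrees with the plan, so the same method is used for QuickSIN.

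**Step 2: direction, without any SD.** Let D = PRO-FIT minus SELF-FIT. SELF-FIT worse by 1.5 dB means D = −1.5; worse by 3 dB means D = −3. Both satisfy D < 1.5. SELF-FIT better by 3 dB means D = +3, which falls in the null. The rule in 3.1.4 thus accepts any deficit and rejects only a large advantage.

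**Step 3: pass probability as written.** SE = SD / √36 = SD / 6, df = 34, critical t = 2.032, noncentrality = (D − 1.5) / SE. The test passes when t falls below −2.032. For SD 3.5 and D = −1.5: SE = 0.583, noncentrality = −3 / 0.583 = −5.14, pass probability 0.9988.

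| True state | As written, 2.5% (SD 2 to 3.5) | Two one-sided tests within ±1.5 dB, 2.5% each |
|---|---|---|
| SELF-FIT 1.5 dB worse | 0.9988 to 1.000 | 0.024 to 0.025 |
| SELF-FIT 3 dB worse | 1.000 | 0.000 |
| SELF-FIT 3 dB better | 0.000 | 0.000 |

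At SD 4 dB, a SELF-FIT 1.5 dB worse still passes with probability 0.992. A non-inferiority test with the sign turned round (SELF-FIT minus PRO-FIT below 1.5 dB) would pass that SELF-FIT 2.5% of the time, as intended.

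**Step 4: power of the two repairs at equal significance level** (N = 36, no true difference).

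| SD (dB) | Level per test | Non-inferiority | Two one-sided tests |
|---|---|---|---|
| 2.5 | 5% | 0.97 | 0.94 |
| 2.5 | 2.5% | 0.94 | 0.88 |
| 3.5 | 5% | 0.81 | 0.62 |
| 3.5 | 2.5% | 0.70 | 0.41 |

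**The case against.** The strongest reply is that non-inferiority was intended and the sign is a drafting slip. Sections 1.5.3.1 and 8.4 say non-inferior for the wear-time trial, and 8.1.5 names that test, which in its ordinary meaning guards against a worse SELF-FIT. Section 5.1 describes the parallel APHAB null as SELF-FIT being inferior, which shows the intended direction. This stands in part: equivalence is not clearly the settled objective, and the reversed sign is in 3.1.4, not in 8.1.5. It does not remove the fault. If non-inferiority was meant, the criterion in the synopsis and 3.2.3 is wrong, and 3.1.4, the only formal statement of the hypotheses for this endpoint, still points the wrong way.

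A reader might go further and infer any of the following, which the documents do not support:
- *The trial could be declared a success wrongly because of this.* Section 8.4 ties overall success to the primary endpoints; wear-time QuickSIN is secondary.
- *The plan would pass a device that harms hearing in noise.* The contrast is with PRO-FIT. SELF-FIT could trail PRO-FIT and still improve on unaided listening, which 6.2.7 measures separately.
- *A large deficit would stay hidden.* Section 8.1.5 also plans to examine the distribution of the dB differences.
- *Two one-sided tests are the only valid repair.* Given 1.5.3.1 and 8.4, a correctly signed non-inferiority test is equally open.

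**Conclusion.** The point holds for a secondary endpoint. The plan gives two incompatible objectives for wear-time QuickSIN, and under either one the hypotheses in 3.1.4 are wrong as written. Applied literally, they would pass a SELF-FIT at the margin of 1.5 dB worse about 99.9% of the time or more, and one at twice the margin essentially always. Those percentages assume N = 36, one-sided 2.5% and an SD of 2 to 3.5 dB, of which only N is stated for this study as a whole. The direction error itself rests only on the score definition and the inequality in 3.1.4. The consequence is confined to the secondary speech-in-noise claim.

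**What to change.** Before analysis, choose one objective and make the synopsis, 1.5.3.1, 3.1.4, 3.2.3, 8.1.5 and 8.4 agree. State the contrast, margin and significance level in 8.1.5.

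(a) **Equivalence.** Use two one-sided tests of the sequence-adjusted mean SELF-FIT minus PRO-FIT crossover contrast against −1.5 and +1.5 dB, and change the non-inferiority wording in 1.5.3.1 and 8.4 for this endpoint. The symmetric margins remove the sign problem. The cost is power at the same significance level when the SD is large: at 3.5 dB, a loss of 19 points at 5% (81% to 62%) or 29 points at 2.5% (70% to 41%). At 2.5 dB it is 3 points (97% to 94%) or 6 points (94% to 88%). This option would also fail a SELF-FIT that is clearly better.

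(b) **Non-inferiority.** Change the criterion in the synopsis and 3.2.3, and write the null as SELF-FIT minus PRO-FIT at or above 1.5 dB and the alternative as below 1.5 dB. This is wording only, with no loss of power.

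Neither option adds subjects, visits or measurements.

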8.2 Interim Analysis

No interim analysis will be performed for this investigation.

8.3 Missing Data Management

All planned data will be collected as complete and as timely as possible. No imputation of missing data is anticipated.

8.4 Pass/Fail Criteria of the Study

For the in-lab session, the primary effectiveness endpoint will be assessed by the differences in acoustical real-ear aided gain (REAG), a gold-standard measure for the acoustical function of hearing devices for the study population. This endpoint will be used to assess mean absolute-value differences between two replications of the self-fit method (reliability) and between the self-fit and professional-fit methods (validity or effectiveness).

For the wear-time trial, the primary outcome measure is a widely used clinical self-report measure of benefit (Abbreviated Profile of Hearing Aid Benefit, APHAB). The APHAB is also a gold-standard, validated assessment of hearing-aid benefit relevant for the study population.

Secondary effectiveness endpoints for both the laboratory and field-trial components will be assessed by a standardized measure of speech communication in noise, the QuickSIN. This is a widely used clinical measure of an adult's ability to understand speech in noise and is closely tied to the wearer's primary complaint, difficulty communicating in noise.

Overall study success will be defined by meeting all primary endpoints for the reliability, effectiveness, and safety of the devices and the self-fitting process in the laboratory and field-trial components of this study. Effectiveness outcomes from the SELF-FIT process should be equivalent to those of the PRO-FIT method in the in-lab session and non-inferior to PRO-FIT in the wear-time trial for the study to be considered successful.

9.0 DEVIATIONS

9.1 Management of Protocol Deviations

A CIP deviation is any noncompliance with the CIP, ISO 14155 Good Clinical Practice (ISO GCP), or Manual of Procedures requirements. The noncompliance may be either on the part of the subject, the site investigator, or the study site staff. As a result of deviations, corrective actions are to be developed by the site and implemented promptly. These practices are consistent with ISO 14155 GCP 9.6 Compliance with the CIP and 8.1 Clinical quality Assurance and Quality Control.

There are two types of CIP deviations, critical deviations and non-critical deviations. All deviations must be documented and reported, the criticality of the deviation will determine the reporting path.

Critical Deviations: Deviations that significantly affect the safety, effectiveness, integrity or conduct of the study. These deviations must be reported to the Sponsor no later than 5 working days from awareness of occurrence and reported to the IRB per the deviation reporting policy.

Note: If an Investigator uses a device without obtaining informed consent, the Investigator shall consider this a critical deviation and report the event to the Sponsor and the IRB within 5 working days of the occurrence.

Non-Critical Deviations: CIP deviations that do not significantly affect the safety, effectiveness, integrity or conduct of the study are considered non-critical deviations. These deviations must be documented and will be reviewed by the study monitor.

It is the responsibility of the site investigator to use continuous vigilance in order to identify deviations. All deviations must be addressed in study source documents with explanations as well as reported to GN Hearing A/S as soon as possible. CIP deviations must be sent to the reviewing IRB per their policies. The site investigator is responsible for knowing and adhering to the reviewing IRB requirements.

The site investigator is not allowed to deviate from the CIP without prior authorization received from the Sponsor, except under emergency situations when necessary to preserve the rights, safety, or well-being of investigation subjects. In the event the deviation involves a failure to obtain a subject's consent or is made to protect the life or physical well-being of a subject in an emergency, the deviation must be reported to the IRB as well as GN Hearing A/S as soon as possible but no later than five (5) working days from the date of the deviation occurrence.

[name] is responsible for analyzing deviations, assessing their significance, and identifying any additional corrective and/or preventive actions which may include amending the CIP, conducting additional training, terminating the investigation, etc. Repetitive or serious investigator compliance issues may represent a need to initiate a corrective action plan with the investigator and site, and in some cases, necessitate suspending enrollment at that site until the problem is resolved or ultimately terminating the site investigator's participation in the study.

10.0 COMPLAINT HANDLING AND ADVERSE EVENT REPORTING

10.1 Foreseeable Adverse Events and Device Effects

Adverse events (AEs) are expected to be extremely rare based on the low risk profile of the device. In rare cases, it is foreseeable that study subjects may experience moderate to mild and typically spontaneously resolving:

- Psychological distress or exacerbation of existing psychological or anxiety conditions, related to the requirements of various features of the device
- Effects related to mechanical interaction with the device, such as eye strain leading to headaches or in rare cases blurred vision, strain of the digits, or transient discomfort

For the purposes of this study, the following will not be considered or reported as AEs:

- Unchanged, chronic, non-worsening of a pre-existing conditions
- A planned hospitalization for pre-existing condition, any outpatient medical or surgical procedures, or hospitalization due to an elective surgery planned prior to screening/baseline visit
- Stable, intermittent chronic conditions present prior to screening/baseline visit that do not worsen during the study
- Outpatient medical or surgical procedures planned prior to screening/baseline visit

As with any medical device that involves electronic transfer of subject data, use of the device may pose risk to study subject privacy. These risks have been mitigated by design to levels considered As Low as Possible in compliance with ISO 14971:2019 Medical Devices – Application of risk management to medical devices.

These foreseeable risks are not elevated beyond levels that would have occurred within the study subject's standard care. The site investigator or designee will be responsible for determining whether an adverse event is foreseeable or not foreseeable. An AE will be considered not foreseeable if the nature, severity, or frequency of the event is not consistent with the risk information previously described for the study.

As in any medical device study, defects may be discovered during testing of the medical device. All defects will be documented during the course of the study as per ISO 14155 and applicable CFR requirements.

10.2 Adverse Event Definitions

An **Adverse Event (AE)** is any untoward medical occurrence in a clinical investigation subject receiving investigational treatment, which does not necessarily have a causal relationship with this treatment. An AE can therefore be any unfavorable and/or unintended sign (including an abnormal laboratory finding), symptom, or disease temporally associated with the use of an investigational medical device, whether or not related to the investigational medical device. Section 1.5, Device Risk Analysis contains a list of foreseeable AEs and adverse device effects. Specific adverse event protocols are defined the by IRBs at Vanderbilt University/Northwestern University, and Sertoma Speech and Hearing Center; however, these protocols are consistent with the following. In addition, Device Risk Assessments and determinations will be performed by the appropriate committees at Vanderbilt and Northwestern Universities as well as Sertoma Speech and Hearing Center.

Treatment-Emergent AEs are AEs that are new-onset, or worsen in severity, and are not anticipated due to the nature of this study and device.

A **Serious Adverse Event (SAE)** is defined as any untoward medical occurrence that either:

- results in death
- is life threatening
- requires inpatient hospitalization or prolongation of existing hospitalization
- results in persistent or significant disability/incapacity (disability is defined as a substantial disruption of a person's ability to conduct normal life functions)
- results in a congenital anomaly/birth defect
- requires intervention to prevent permanent impairment or damage
- results in an important medical event

Device issue or deficiency is an inadequacy of a medical device related to its identity, quality, durability, reliability, safety, or performance, such as malfunction, misuse, or use error and inadequate labeling.

An **Adverse Device Effect (ADE)** is an AE related to the use of an investigational medical device. This definition includes AEs resulting from insufficient or inadequate instructions for use, deployment, implantation, installation, or operation, or any malfunction of the investigational medical device. The definition also includes any event resulting from use error or from intentional misuse of the investigational medical device.

Unanticipated Adverse Device Effect (UADE) means any serious adverse effect on health or safety or any life-threatening problem or death caused by, or associated with, a device, if that effect, problem, or death was not previously identified in nature, severity, or degree of incidence in the investigational plan or application (including a supplementary plan or application), or any other unanticipated serious problem associated with a device that relates to the rights, safety, or welfare of subjects, according to 21 CFR 812.3.

